IMMUNOLOGIC CORRELATES OF NAI: Little is currently known about the underlying mechanisms of NAI. The only studies that have clearly documented in humans the importance of a specific arm of the immune system in protection against malaria have been the classical studies of passive transfer of purified immunoglobulin (Ig) in which transfer of pooled γ -globulin from West African immune adults into East African or Thai children acutely infected with P. falciparum caused a sharp drop in parasitemia [14, 15, 16, 17]. Despite years of studies of human immune response to defined Plasmodium sp. antigens, aiming to correlate a response with apparent clinical status and thus to identify a protective role for that response, it has not been possible to define with any certainty which antigens contribute to NAI, nor to identify any immune response which correlates with NAI. Given the complexity of the parasite and the multitude of immune responses which may be involved, it is unlikely that a single immune response directed against a single antigen expressed during one stage of the parasite's life cycle is responsible for protection. Most studies have only looked at responses against single antigens, including MSP-1 [18, 19, 20], LSA-1 [21], CSP [22], and MSP-3 [16]. Moreover. studies have been limited in that they have not identified and controlled for the many potential confounding factors, including exposure, and in many cases, age. Several studies conducted in the 1970's and 1980's in West Africa focused on longitudinal follow-up of serological responses in infants [23, 24, 25] and older children [26] receiving anti-malarial prophylaxis, but these studies did not control for age or exposure.

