The three cohorts are proposed in order to address the **central hypothesis**: Exposure to Pf erythrocytic stage antigens in early infancy does not contribute to the development of naturally acquired immunity to malaria but exposure after 5 months of age does contribute to the development of naturally acquired immunity. Specifically, the three cohorts are needed to address the following:

1- The comparison of Cohort 1 (prophylaxis 2-5 2,5-5,5 months) and Cohort 2 (prophylaxis 5-10

5,5-10,5 months) is the key comparison. During the first 10 months of life, we assume that both Cohorts 1 and 2 will have experienced exposure to Pf blood stage parasites, and therefore Pf erythrocytic stage antigens, since each have been left unprotected by prophylaxis during several months. We recognize that infants in the first 5 months of life are likely to have a greater degree of protection due to maternal antibodies than those who are 5-10 months of age, although there is some controversy with regard to this [72]. Nevertheless, previous data from our study site indicate that there is essentially no malaria in the first two months of life but that after 2 months, the age-specific incidence of clinical episodes of malaria increases to levels near that of the second year of life. We also recognize that younger infants may be kept more covered by their mothers and thus experience less exposure to mosquitoes. Thus, the rate of malaria acquisition in the two cohorts may not be the same. Because this will be an uncontrolled variable that may affect the outcome measures of the

Final protocol: 2nd July 2004 Amendment 1: 15th October 2004 Amendment 2: 2nd December 2004 Amendment 3: 11th July 2005 Amendment 4: 10th August 2005 Amendment 5: 12th September 2006 CONFIDENTIAL

Page 17 of 51

[figure not shown]
study, the effects of the number of episodes of parasitemia will be included in the statistical model used for analysis (see below). (Amended 2 December, 2004)

[figure not shown]

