Active case detection: Active case detection will consist of a weekly visit by the field worker to the home of the infant *from enrollment until 10,5 months of age*. During this visit an axillary temperature will be taken by electronic digital thermometer and the caretaker(s) will be questioned about any history of fever. In the case of a documented fever (axillary temperature $\geq 37.5^{\circ}$ C) or history of fever in the previous 24 hours, thick and thin blood smears will be collected, stained, and read according to quality-controlled procedures [9]. If there is no fever or history of fever, no sample will be taken. The purpose of this active case detection follow-up is to detect the first encounter with the parasite that produces clinical malaria during the first 10 months of life, the period of the intervention. The respiratory rate of the child will also be recorded, and if increased (>=60 breaths/min in children younger than 2 months and >=50 in children aged 2-12 months), the child will be taken to the health post the mother/guardian will be advised to take the child to the health post if it persists. During these weekly visits, the field worker will also inquire as to whether the child has been hospitalized for any reason or if any skin rashes (potentially indicative of adverse reaction to SP) or other signs/symptoms have developed. (Amended 2 December, 2004) (Amended 11 July, 2005)

Passive case detection: Caretakers will be asked to bring infants into the IIha Josina Maragra health post or the Manhiça health center, where a morbidity surveillance system is functioning, whenever the child is ill. We propose to only enroll families who live within close access to the IIha Josina Maragra or Manhiça health post so that they will all have access to the health facility if they wish to seek care for their children. (Amended 15 October, 2004) (Amended 10 August, 2005)

Monthy surveillance home visits: Home visits will be performed monthly from month 10.5 to month 24 of age. Parents/guardians will be asked about the health status of the child and whether he/she has been admitted to hospital since the previous visit. These visits will ensure that safety information on serious adverse events and deaths is captured. (Amended 11 July, 2005)

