1. Birth, 5, 10, 12, 15, 20 and 25 months of age *Birth or enrolment* - *Cross sectional cord blood samples* for parasitological, *host genetics, full blood count full blood count (FBC)* and immunological studies.

2. 2,5 months of age – Cross sectional samples for haematocrit FBC, filter paper, host genetics and immunological studies.

2. 3. 5,5; 10,5 and 15 months of age – Cross sectional samples for immunological studies and FBC. If the child has fever, blood will also be taken to determine parasitaemia and haematocrit.

3. 4. 24 months of age – Cross sectional samples for parasitological (blood smear and filter paper), complete blood count haematocrit FBC and immunological studies.

2-4. 5. Time of first infection and one month later - Acute and convalescent samples for parasitological and immunological and immunological and immunological studies will be drawn at the time of the first documented clinical episode and one month later.

3 5. 6. All subsequent clinical episodes until 25 24 months of age - Acute samples for parasitological studies only.

(Amended 2 December, 2004) (Amended 11 July, 2005) (Amended 10 August, 2005)

Collection of samples at birth will be as follows:

Maternal: 5 ml 10 mL venous blood for Het *FBC*, thick and thin blood smear for detection of parasitemia, and *immunological studies, including* measurement of maternal antibodies, *and host genetics of the mother (same genotypes measured in offspring will be measured in the mother)*. In addition, tissue and blood samples of the placenta will be collected [73] to determine whether there is placental sequestration and to evaluate the genotypes of any sequestering parasites. A biopsy of 2.5-cm² will be cut from the maternal surface in an off-center position (in an area without evidence of infarction), halfway between the umbilical cord and the edge of the placenta, and placed in 25 ml of 10% neutral buffered formalin. The remaining placental specimens will be kept at 4°C, embedded in paraffin wax using standard techniques, and a 4 µm thick section will be stained with hematoxylin and eosin, or Giemsa and perodic acid-Schiff for standard histological evaluation and quantification of parasites and malaria pigment. The placental blood sample will be collected onto filter paper and used for PCR diagnosis of placental parasitemia and genotyping.

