The primary aim of the study is to determine the effect of timing of exposure to Pf erythrocytic stage antigens during infancy (0 to 5 vs 5 to 10 months of age) on subsequent morbidity due to clinical malaria. The primary outcome variable was chosen as the presence or absence of at least one episode of clinical malaria during the second year of life **as detected by passive case detection**, because current epidemiological data suggests that this outcome is a sensitive, inverse indicator of NAI; when used as the primary outcome variable in studies detailed earlier in this proposal (see background and rationale sections) significant differences were detected between cohorts receiving differing prophylaxis [1, 2]. In the study site, an incidence of **0.4 0.48**-episodes of clinical malaria per person year at risk ([name], personal communication). Thus, as described in the sample size section, each of the three cohorts will be compared to the others in pairwise fashion, with the p value for significance reduced to 0.017 to adjust for the three comparisons. **(Amended 15 October, 2004) (Amended 2 December, 2004)**

However, other variables could also affect the likelihood of experiencing at least one clinical episode during the second year of life, such as number of clinical episodes experienced during the first year of life, regardless of the age at which they occurred. In addition, we believe that immunological responses during the first year of life may potentially explain the differences in susceptibility to clinical episodes during the second year (secondary aim), although other factors, such as host genotype (e.g., presence or absence of sickle cell trait, α -thalassemia or others), the presence of haemoglobin AF, parasite genotype, and possibly maternal immune responses, could also affect the primary outcome variable. Because we do not know which of these many factors will be most closely associated with the outcome, we propose a logistic regression analysis to make this assessment. All of these factors will be used in a multiple logistic regression model, and those with significant associations will be identified. Although it is by no means assured, we hope that one of the immunological measurements (see below) will show a significant association and thus will serve as a positive or negative correlate with NAI. A rationale has been provided regarding the concentration of antibody responses to PfEMP-1 as a likely candidate.

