Our prediction: We hypothesize that the level of antibodies will be statistically significantly lower in Cohort 2 as compared to either Cohort 1 or Cohort 3 at the 10 month old cross-samplings and that this reduction will correlate with an increased relative risk of one or more clinical episodes of malaria in the second year of life.

Proposed analysis: Immunological endpoints will be based upon levels of antibodies (intensity) and the ratio of Th1/Th2 cytokines at each of the cross-sectional time points. For the first analysis, values for antibodies and cytokine ratios for each cohort will be compared at each cross-sectional timepoint. For the second analysis, values for antibodies and cytokine ratios at each of the timepoints will be correlated with risk of clinical outcome(s) for each cohort and between cohorts. Immunological data will be analyzed in two different ways:

- **Cross-sectionally** the key analysis will be comparison of immunological markers between cohorts, not individuals, to show differences in the development of acquired immunity to malaria attributable to age of first exposure to Pf antigens. The key timepoint for comparison is considered to be 10 months. We will explore the profile of immune responses and how markers change with age. Specifically, we predict the following outcomes:

X1; t= 2,5 month 0 or enrollment. No difference between the 3 cohorts

X2, t=5 5,5 month: No difference between the 3 cohorts

X3, t=10 10,5 month (*key comparison*): Cohort 2 will have significantly lower levels of anti-PfEMP-1 antibodies and/or Th1/Th2 cytokine ratios than cohort 1 and 3. Cohort 1 = cohort 3. **X4**, t=12 month: same as X3.

X5- **X4**, t=15 month: same as X3.

X6, t= 20 month: No difference between the 3 cohorts.

X7- **X5**, t= 25 **24** month: same as X6. We expect the immune responses to equalize between cohorts by 20-25 months.

(Amended 2 December, 2004) (Amended 11 July, 2005)

- **Prospectively**: To look for correlates of immune responses and clinical outcome. Specifically, acquisition of immune response at the level of the individual subject (as opposed to cohort) in cohort 1 vs. 2, and correlation with how that individual responds to infection and the relative risk of clinical disease. We will evaluate whether lack of exposure at different ages (0-5 months, or 5-10 months) during first 2 years of life results in differences of antibody and/or cytokine markers between the different cohorts.

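### The exploratory marker-risk analyses adjust for exposure only through a sparse, symptom-driven episode count and accept an association of either sign, so a marker of exposure can be labelled a correlate of immunity

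*Protocol*

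**What the plan says.** Section D.xi.1.a (Overall Analytical Plan) lists variables that might affect whether a child has malaria in the second year: immune responses, host and parasite genotype, maternal responses, and exposure-related history, "such as number of clinical episodes experienced during the first year of life, regardless of the age at which they occurred". It continues: "All of these factors will be used in a multiple logistic regression model, and those with significant associations will be identified". The authors then hope that an immunological measurement "will show a significant association and thus will serve as a positive or negative correlate with NAI".

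Section D.iii (Rationale for the 3 cohorts) names a different count. Because infection may be acquired at different rates in Cohorts 1 and 2, "the effects of the number of episodes of parasitemia will be included in the statistical model used for analysis".

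Section D.xi.2.a relates marker values at each timepoint to clinical risk and, for individual children, plans "correlation with how that individual responds to infection and the relative risk of clinical disease". It names no exposure term. It predicts that lower antibody at 10 months goes with higher risk, and it makes the between-cohort comparison of markers the key analysis.

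Section A (Immunologic correlates of NAI) criticises earlier studies because "they have not identified and controlled for the many potential confounding factors, including exposure". The same background section expects anti-GPI antibodies to be especially dependent on exposure, and D.viii makes them a primary immunological outcome.

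**The concern.** Randomisation protects comparisons between cohorts. It does not protect a comparison of high-marker with low-marker children inside a cohort. A child who is bitten often tends to have more antibody and more later malaria. A child who is rarely bitten tends to have little of either and is scored as if immune. Exposure therefore pushes marker associations towards higher risk.

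A rule that accepts significance of either sign would call such a marker a negative correlate of NAI. The same bias can cancel or reverse the association of a marker that does protect. This is the weakness that the protocol finds in the earlier literature, and it expects at least one of its own markers to be exposure-dependent.

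What is at stake is objective (iii) of the immunology sampling, the search for correlates of second-year risk. The primary aim is not at stake.

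**Working it through.** **Planning figures.** The protocol gives no figure for the correlate analysis. Its sample size does reproduce, which confirms the planning rates. For two Poisson rates, n = (z₁ + z₂)²(r₁ + r₂)/(r₁ − r₂)². With r = 0.4 and 0.8 per year, two-sided α = 0.017 and 80% power, n = (2.387 + 0.842)² × 1.2/0.16 = 78.2, against 78 stated; 78/0.8 = 97.5, so 98. After Amendment 5, 350 × 0.8 = 280 evaluable children, about 93 per cohort.

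**How much the count can carry.** Inputs are the age-specific rates in the Manhiça table (D.i), with 4.348 weeks per month:

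| Age window (months) | Calculation | Expected episodes, no drug |
|---|---|---|
| 2.5–5.5 | 3 × 4.348 × 35/9491 | 0.048 |
| 5.5–10.5 | 0.5 × 4.348 × 35/9491 + 2 × 4.348 × 46/6134 + 2.5 × 4.348 × 117/12963 | 0.171 |
| 10.5–12 | 1.5 × 4.348 × 117/12963 | 0.059 |

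The sum is 0.22 to 10.5 months and 0.28 to 12 months. The Poisson share of zeros is e^(−0.219) = 80% and e^(−0.278) = 76%. The 12-month figure is an upper one, because the table comes from weekly active visits and the trial's active detection stops at 10.5 months. If study drug removed all episodes in its window, the 12-month means would be 0.171 + 0.059 = 0.23 in Cohort 1 and 0.048 + 0.059 = 0.11 in Cohort 2. Amendment 5 reports lower incidence than expected, which means still more zeros.

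**What the count measures.** At home visits, "If there is no fever or history of fever, no sample will be taken" (D.iv). At 5.5, 10.5 and 15 months blood for parasitaemia is also taken only if the child has fever (D.vi). During the intervention period the parasitemia count of D.iii thus nearly collapses into the clinical count of D.xi.1.a. Since symptoms depend partly on immunity, neither is a clean measure of exposure. Neither covers second-year exposure. Routine parasitology comes back only at 24 months ("Cross sectional samples for parasitological (blood smear and filter paper"), at the end of the outcome period.

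**Effect on the marker analysis.** This is simulation; exposure heterogeneity and marker-exposure correlation are assumptions. Each child has a log-normal exposure, a marker correlated with it, a Poisson first-year count and a second-year outcome analysed by logistic regression (two-sided 0.05). The settings below are 280 children, a second-year rate of 0.4, a first-year mean of 0.22 multiplied by an assumed 0.8, 0.45 and 1 in Cohorts 1, 2 and 3, and 1,000 runs each.

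Marker with no protective role, share of trials with a significant association with higher risk (OR per SD):

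| Exposure CV, correlation | Unadjusted | Count + cohort | True exposure |
|---|---|---|---|
| 0.5, 0.3 | 26% (1.19) | 25% (1.18) | 3% (1.00) |
| 1.0, 0.5 | 92% (1.58) | 86% (1.53) | 2% (1.00) |
| 1.5, 0.7 | 100% (2.29) | >99% (2.15) | 3% (1.00) |

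Marker that lowers the malaria rate by 30% per SD, share of trials finding it protective (OR per SD):

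| Exposure CV, correlation | Unadjusted | Count + cohort | True exposure |
|---|---|---|---|
| 0.5, 0.3 | 49% (0.78) | 51% (0.77) | 87% (0.64) |
| 1.0, 0.5 | 1% (1.06) | 1% (1.03) | 75% (0.64) |
| 1.5, 0.7 | 0% (1.54) | 0% (1.43) | 52% (0.64) |

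For the narrower range of log-exposure SD 0.5 to 1.0 (CV = √(e^(SD²) − 1) = 0.53 to 1.31) and correlation 0.3 to 0.5, false associations occur in about 31–99% of trials with cohort alone and 28–94% with cohort and the count. Adding area lowers this to 18–80%, if area explains a quarter of the exposure variance (also an assumption).

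**The case against.** The strongest reply is that the plan does adjust for exposure. D.xi.1.a places the first-year episode count in the same model as the markers, and D.iii promises a parasitemia count. A reader might infer from the criticism of earlier studies that this trial repeats their fault with no exposure control at all; the documents do not support that. What survives is that the adjustment is too weak.

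Second, the sentence about correlates is worded as a hope in an exploratory search, and D.xi.2.a predicts a direction for antibodies. This stands against reading the text as a certainty that exposure markers will be reported and protective ones missed. But the prediction is a hypothesis, not a condition for naming a correlate, and it does not govern cytokine ratios or anti-GPI as predictors of risk.

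Third, D.xi.2.a makes the randomised between-cohort comparison the key immunological analysis. A reader might infer that the immunology as a whole is compromised; it is not, since individual exposure does not bias that comparison.

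Fourth, an association with higher risk need not reflect exposure: the section on host age mentions antibody isotypes that may block protective ones. That stands, and it shapes the fix.

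Finally, covariate detail is often left to an analysis plan. The reading rule and the choice of count, however, are stated in the protocol.

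**Conclusion.** The concern holds for the exploratory individual-level analyses only. Significance of either sign, with a mostly zero, symptom-driven and drug-suppressed count as the sole exposure term, cannot separate a marker of exposure from a correlate of protection. In simulation the count removes little of the bias: false associations fall only from about 31–99% to 28–94% with cohort in the model.

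These percentages show what can happen. They rest on an assumed log-exposure SD of 0.5 to 1.0 and correlation of 0.3 to 0.5, neither of which the protocol gives; with little heterogeneity or weak correlation the problem shrinks. The sparseness of the count rests on the protocol's own rates. The randomised clinical comparison and the between-cohort marker comparison are untouched by this confounding.

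**What to change.** 1. In D.xi.1.a, call a marker a candidate correlate of protection only if it is associated with lower later risk after exposure adjustment. Report an association with higher risk as a possible marker of exposure, not as evidence about immunity either way.
2. Reconcile the counts in D.iii and D.xi.1.a. In every marker-risk model in D.xi.1.a and D.xi.2.a, include cohort, area (Maragra or Manhiça), month of birth and the agreed count. Keep that count out of the randomised cohort comparison, because it arises after randomisation.
3. State that residual exposure confounding remains. These covariates reduce it but cannot be expected to remove it.

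An analysis restricted to children with evidence of infection in the second year may look attractive. It should be left out or labelled exploratory: every clinical case enters through the outcome itself, whereas a non-case enters only through a single 24-month sample.

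The cost is wording, a few more model terms, and fewer markers that can be claimed as correlates. No new data are needed.
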